2 INTRODUCTION

SAR440340 (also known as REGN3500 or R3500) is a human monoclonal antibody (mAb) that targets IL-33 and is under development as a potential novel treatment for both asthma and COPD.

2.1 STUDY RATIONALE

Chronic obstructive pulmonary disease (COPD) is a highly prevalent disease worldwide that is associated with significant economic burden and for which available standard-of-care therapy shows insufficient efficacy on symptoms, lung function, exacerbations and long-term evolution of the disease. IL-33 is a pro-inflammatory cytokine that initiates and amplifies innate and adaptive inflammatory cascades in response to epithelial cell stress or damage due to exposure to airborne allergens, viruses, cigarette smoke, and air pollutants. The objective of the current study is to investigate the effects of 300 mg SAR440340 administered SC once every 2 weeks as compared to placebo on reducing the incidence of exacerbations in patients with moderate-to-severe COPD.

2.2 BACKGROUND

2.2.1 Chronic obstructive pulmonary disease

Chronic obstructive pulmonary disease (COPD) is a heterogeneous syndrome associated with an abnormal inflammatory immune response of the lung to noxious particles and gases (1). Chronic inflammation causes structural changes, narrowing of the small airways, and destruction of the lung parenchyma that leads to the loss of alveolar attachments to the small airways and decreases lung elastic recoil. It results in progressive airflow obstruction that is only partly reversible or even irreversible. The inflammation component of COPD is thought to involve many cell types including structural cells, T lymphocytes, neutrophils, macrophages, and their biological products. In some patients, there may also be an increase of eosinophils, T-helper (Th) 2 or Group 2 Innate Lymphoid cells, especially where there is clinical overlap with asthma. The main cause of COPD is smoking tobacco, but other factors have been identified, such as air pollution, occupational exposure, and genetic susceptibility. The most common respiratory symptoms include chronic dyspnea, cough and/or sputum production. The disease is further aggravated by exacerbations, particularly for severe COPD. These are most often due to viral and bacterial infections of the lungs which trigger the inflammatory response, tissue destruction, and the resultant hypoxia. Exacerbations in COPD patients are associated with rapid disease progression (rate of lung function decline over time) and increased risk of mortality. Medical comorbidities such as cardiovascular disease, diabetes, lung cancer, skeletal muscle dysfunction, osteoporosis, psychological disturbances, and metabolic syndrome are common among COPD patients and occur across the spectrum of disease severity.

Chronic obstructive pulmonary disease is a highly prevalent, serious and progressive disease resulting in significant morbidity, mortality, and economic burden (2, 3). In the US alone there are more than 12 million diagnosed patients and the incidence of COPD is expected to grow rapidly with an aging population. COPD is a progressive and irreversible inflammatory lung disease that is periodically punctuated by disease exacerbations that result in long term disability and

mortality. Globally there are around 3 million deaths attributed to COPD annually. With the increasing prevalence of smoking in developing countries, and aging populations in high-income countries, the prevalence is expected to rise and the number of deaths to reach 4.5 million by 2030.

The standard of care for moderate COPD starts with bronchodilators (such as long-acting muscarinic antagonists [LAMA] or long-acting β_2 agonists [LABA]), and as disease progresses bronchodilators are combined with other drugs such as inhaled corticosteroids (ICS), and phosphodiesterase type 4 (PDE-4) inhibitors (roflumilast) (4, 5, 6). The major limitations of the existing agents for COPD include modest efficacy and risk of respiratory infections (ICS). Oral or systemic corticosteroids are reserved for treatment of exacerbations given their unacceptable long-term safety profile in the COPD population. No approved therapeutic agent blocks the decline in forced expiratory volume in 1 second (FEV1) over time or modifies the progressive disease course of COPD. Thus there is a high unmet need for more effective treatment of this disease.

Currently, no targeted biological treatments addressing the immunological underpinnings of COPD are approved. The anti-interleukin (IL)-5 mAb mepolizumab shows a modest 18%-20% reduction of exacerbations in COPD patients with high blood eosinophils. The anti-IL-5 receptor mAb benralizumab is still in Phase 3 clinical trials, and preliminary data from Phase 2a trial suggest that the FEV1 improvement versus placebo averaging approximately 150 mL over time is mainly driven by the subgroup of patients with high blood eosinophils. In this study, no reduction of exacerbations was seen in the per-protocol population, and a numerical, but not statistically significant, reduction of exacerbation was seen in the subgroup of patients with high blood eosinophils (7, 8).

Thus, significant unmet medical needs continue to exist in the growing population of patients with COPD. The main objective for new treatments is to further improve COPD symptoms, lung function, and prevent exacerbations, while optimizing adherence to the treatment.

2.2.2 SAR440340 - Anti-IL-33 monoclonal antibody

SAR440340 is a human mAb that targets IL-33. IL-33 is a proinflammatory cytokine that initiates and amplifies innate and adaptive inflammatory cascades (9) in response to epithelial cell stress or damage (“alarmin”) due to exposure to airborne allergens, viruses, cigarette smoke, and air pollutants. Accumulating evidence from human studies and animal models suggests that IL-33 is potentially implicated in the pathogenesis of COPD, and provides the rationale for the use of SAR440340 in patients with COPD. Studies from the Regeneron Genetics Center provide evidence that genetic variation in the IL-33 and IL1RL1 genes are common risk factors for COPD. In humans, increased levels of IL-33 have been reported in bronchial cells of COPD patients (10, 11). It is also known that IL-33 protein expression in the lungs correlates with COPD severity and is a negatively correlated with FEV1 (11). A separate study has found that plasma IL-33 level in patients with stable COPD was related to eosinophil count and chronic bronchitis phenotype (12). Supporting data from a preclinical murine smoking model of COPD suggests a dual role for IL-33 in amplifying lung inflammation during viral exacerbations of COPD. Initially, smoke inhalation upregulates intracellular IL-33 in mice, as well as the proportion of epithelial cells expressing IL-33; secondly, viral infection leads to focal cellular necrosis, release of IL-33, and increased production of proinflammatory cytokines such as IL-6 and tumor necrosis factor- α

(TNF- α) in the lung (11). Therefore, it is hypothesized that blockade of IL-33 which is locally released in the airway in the setting of environmental triggers such as infection or toxic inhalants may be a novel therapeutic approach to prevent exacerbations.

2.3 BENEFIT/RISK ASSESSMENT

The Phase 1 study in healthy subjects suggests that SAR440340 is well-tolerated at doses up to 10 mg/kg administered IV as single dose. Unblinded safety data from the ongoing multiple ascending dose study (R3500-AS-1619, data as of February 23, 2018) in asthma patients have demonstrated that weekly doses of 75 mg and 150 SC are so far well tolerated. No SAEs or deaths have been reported in any of the Phase 1 studies. SAR440340 is expected to inhibit the proinflammatory activity of IL-33, which is elevated in COPD patients. Thus, the benefit/risk profile for SAR440340 in this study supports its evaluation as a potential agent for treatment of COPD.

There is a potential risk of infection associated with blocking of host defense pathways by SAR440340. The preliminary safety data from the first in human (FIH) study of SAR440340 have revealed no safety signals. Therefore, the anticipated safety of SAR440340 is considered reasonable, with close monitoring of adverse events (AEs) and laboratory results throughout the study and follow-up period. The safety data and other potential risks (systemic hypersensitivity, embryo-foetal toxicity, immunogenicity) for SAR440340 are summarized in the Investigator's Brochure (IB).

3 OBJECTIVES AND ENDPOINTS

Table 1 - Objectives and endpoints

Objectives	Endpoints
Primary	

 To investigate effects of SAR440340 (anti-IL 33 mAb) compared with placebo, on the annualized rate of moderate-to-severe acute exacerbations of COPD (AECOPD) over up to 52 weeks of treatment. 	
 Annualized rate of moderate*-to-severe** AECOPD over the treatment period. 
*Moderate exacerbations are recorded by the Investigator and defined as AECOPD that require either systemic corticosteroids (such as intramuscular, intravenous or oral) and/or antibiotics. ** Severe exacerbations are recorded by the Investigator and defined as AECOPD requiring hospitalization, emergency medical care visit or resulting in death.

Secondary	

 To investigate effects of SAR440340 compared with placebo, on improving respiratory function, as assessed by pre bronchodilator FEV1 over 24 weeks. 	
 Average change from baseline to Week 16-24*** in FEV1 (pre-bronchodilator) 
*** Model-based averages across Weeks 16, 20 and 24 will be compared between the treatment groups

 To evaluate effects of SAR440340 compared with placebo, on Post-bronchodilator FEV1 over 24 weeks 	
 Change from baseline to Week 24 in FEV1 (post-bronchodilator****) 
**** Post-bronchodilator means 30 minutes after either 400 mcg of salbutamol/albuterol (4 puffs of 100 mcg each) or 80 mcg of ipratropium bromide (4 puffs of 20 mcg each).

 To evaluate effects of SAR440340 compared with placebo, on duration from baseline to first moderate or severe AECOPD event over up to 52 weeks 	
 Time to first moderate or severe AECOPD.

 To evaluate effects of SAR440340 compared with placebo, on safety and tolerability 	
 Treatment-emergent adverse events (TEAE) Serious adverse events (SAE)
Tertiary/exploratory	

 To evaluate the effects of SAR440340 compared with placebo, on patient reported symptoms and quality of life as documented by e-Diary and utilizing Exacerbations of Chronic Obstructive Pulmonary Disease Tool (EXACT), St. George's Respiratory Questionnaire (SGRQ) and Euroqol-5Dimension (EQ 5D) questionnaire 
 in all patients treated with SAR440340/placebo in subpopulations with high blood eosinophil level (≥ 250 /mm³) and low blood eosinophil level (<250 /mm³) 	
 Change from baseline in the EXACT scores at Week 24 Change from baseline in the SGRQ scores at Week 24 Change from baseline in the EQ-5D scores at Week 24

 To evaluate the pharmacokinetic (PK) profile of SAR440340 in serum 	
 Serum functional SAR440340 concentrations

 To evaluate the effects of SAR440340 Antidrug antibodies (ADA) 	
 Antidrug antibodies (ADA) against SAR440340

 To evaluate the effects of SAR440340 compared with placebo, on FEV1, AECOPD, and other relevant endpoints 
 in subpopulations with high blood eosinophil level (≥ 250 /mm³) and low blood eosinophil level (<250 /mm³) in subpopulations according to use/no use of ICS 	
 Change from baseline to Week 24 in FEV1 (pre-bronchodilator and post-bronchodilator) Rate of moderate-to-severe AECOPD

Objectives	Endpoints
with bronchodilators as background therapy, fibrinogen levels, and smoking status.	

 To evaluate the effects of pharmacogenomics on SAR440340 	
 Future Assessment of DNA or RNA samples for the pharmacogenomics sub study to identify genomic associations with clinical or biomarker response, other clinical outcome measures and possible AEs

 To evaluate the effects of SAR440340 compared with placebo on other respiratory assessments (expanded AECOPD endpoint) 	
 Change from baseline to Week 16-24 in FVC (% predicted and absolute values in mL). Time to the first moderate and severe exacerbations or time to study drug discontinuation (after Week 4) due to lack of efficacy, based on the investigator's judgement (expanded AECOPD endpoint)

 To evaluate the clinical symptoms of COPD in patients treated with SAR440340 versus placebo 
 in all patients treated with SAR440340/placebo in subpopulations with high blood eosinophil level (≥ 250 /mm³) and low blood eosinophil level (<250 /mm³) in subpopulations according to use/no use of ICS with bronchodilators as background therapy, fibrinogen levels, and smoking status 	
 Time to first Clinically Important Deterioration (CID) as defined by decrease of >100 mL from baseline in trough FEV1 and /or deterioration in SGRQ by 4 units and/or moderate-to-severe AECOPD up to Week 24 (and over the 52 week variable treatment period)

 To evaluate the pharmacodynamics effects of SAR440340 	
 Blood eosinophil and neutrophil counts. Levels of biomarkers of the interleukin (IL)-33 and/or Type 2 inflammation pathway 
 Total IL-33, sST2 levels Calcitonin levels PARC levels Eotaxin-3 levels Total IgE levels Fibrinogen levels Induced sputum for RNA expression (optional for patients at a subset of sites). Optional: Messenger ribonucleic acid sequencing or whole transcriptome analysis. Optional: DNA/RNA sample will be collected for pharmacogenomic effects.

 Optional actigraphy (sleep and activity) and home spirometry (available for patients in US and Canada only): To evaluate the effects of SAR440340 compared to placebo on parameters of sleep, activity, and at-home spirometry. 	
 Change from average measurement over baseline (2 weeks prior to randomization) to average measurements over Weeks 10-12 (2 weeks prior to Visit 8) and Weeks 22-24 (2 weeks prior to Visit 14) of sleep and activity parameters. 
 Sleep: Total sleep time, wake after sleep onset, overnight activity counts Activity: Daytime activity counts, percent of time spent in sedentary activity, percent of time spent in moderate to vigorous physical activity Spirometry: FEV1

 Optional actigraphy (sleep and activity) and home spirometry (available for patients in US and Canada only): To compare the utility of at-home spirometry against in-clinic spirometry 	
 FEV1 (Spirometry performed at home) FEV1 (Spirometry performed at the clinic)

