- u* Spirometry will be done locally according to European Respiratory Society (ERS)/American Thoracic Society (ATS) 2005 guidance but measured by a central laboratory. Spirometry will be performed during a trough period of bronchodilators according to their action duration, for example, withholding the last dose of salbutamol/albuterol or levosalbutamol/levalbuterol for at least 6 hours, withholding the last dose of ipratropium for at least 8 hours, withholding the last dose of LABA for at least 12 hours (ultra-long acting LABA like vilanterol should be withheld for at least 24 hours) and withholding the last dose of LAMA for at least 24 hours. This will be verified before performing the measurements. Note: When both pre and post-bronchodilator spirometry is assessed, the post-bronchodilator spirometry should be performed consistent with the mechanism of action of reliever (ie, 30 minutes for albuterol or other SABA).
- v* Following randomization and during the treatment period - if spirometry is not performed at the scheduled visit it should be performed at the following visit during the treatment period.
- w* The EXACT, SGRQ and EQ-5D-5L are to be completed in the patient's electronic diary.

- d* Electronic Diary will be used on daily basis for period of 12 weeks after ETD. The CAT assessment, and reliever medication will not be collected in patients after early treatment discontinuation.
- e* Complete physical examinations will include skin, nasal cavities, eyes, ears, respiratory, cardiovascular, gastrointestinal, neurological, lymphatic, and musculoskeletal systems.
- f* Vital signs, including systolic and diastolic blood pressure (mmHg), pulse rate (beats per minute), body temperature (°C), and respiratory rate will be measured at on-site visits. Body weight (kg) will be measured at EOT/EOS visits.
- g* ECG to be centrally collected & read.

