2.1.3.3 Tertiary efficacy endpoint(s)

- Change from baseline at Week 24 in the patient-reported outcome including EXACT domain and total scores, EQ-5D-5L index score and Visual Analogue Scale (VAS) and SGRQ domain and total scores.
- Proportion of patients with a decrease from baseline of 4 points or more in the SGRQ total score (i.e. change from baseline ≤ -4) at Week 24.
- Average change from baseline to Week 16-24 in FVC (% predicted and absolute values in mL)
- Time to the first expanded AECOPD endpoint (moderate or severe AECOPD or study drug discontinuation [after week 4] due to lack of efficacy) up to week 52
- Time to first Clinically Important Deterioration (CID) as defined by decrease of >100mL from baseline in trough pre-BD FEV1 and/or deterioration in SGRQ by 4 units and/or moderate-to-severe AECOPD over the treatment period

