2.1.3.3.1 Patient-reported outcomes

COPD Assessment Test (CAT)

The CAT is a short, validated, patient-completed questionnaire to assess the impact of COPD on health status (see [Appendix C](#)). It comprises 8 questions that cover a broad range of effects of COPD on patients' health. Each question is scored in a range between 0 (I am very happy) and 5 (I am very sad), with the higher end indicating a higher impact of COPD on the patient's wellbeing. The CAT total score, the sum of the 8 individual question scores, ranges from 0 (best) to 40 (worst). This score is collected only at screening and baseline to assess patient eligibility.

St. George's respiratory questionnaire (SGRQ)

St. George's Respiratory Questionnaire (SGRQ) is a 50-item PRO instrument developed to measure the health status of patients with airway obstruction diseases (see [Appendix E](#)). The questionnaire is divided into two parts: part one consists of eight items pertaining to the severity of respiratory symptoms in the preceding 4 weeks; part two consists of 42 items related to the daily activity and psychosocial impacts of the individual's respiratory condition.

The SGRQ yields a total score and three domain scores (symptoms, activity, and impacts). The total score indicates the impact of disease on overall health status. This total score is expressed as a percentage of overall impairment; 100 represents the worst possible health status and 0 indicates the best possible health status (minimal clinically important difference: -4 units). Likewise, the domain scores range from 0-100, with greater scores indicative of greater impairment. See [Appendix F](#) for the scoring algorithm.

This questionnaire is assessed at baseline and at weeks 4, 8, 12, 24, 36, 52, 60 and 72.

Exacerbations of chronic obstructive pulmonary disease tool (EXACT)

The EXACT is a 14-item daily diary designed to provide a direct measure of patient-reported symptoms of COPD exacerbation (see [Appendix B](#)) and covers the following domains:

- Breathlessness (5 items),
- Cough and sputum (2 items),
- Chest symptoms (3 items),
- Difficulty bringing up sputum (1 item),
- Tired or weak (1 item),
- Sleep disturbance (1 item), and
- Scared or worried (1 item).

It is completed each evening before bedtime.

The EXACT total score is an interval-level scale ranging from 0 to 100, where higher scores indicate a more severe condition.

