Time to first moderate or severe AECOPD is defined as (onset date of the first moderate or severe AECOPD-randomization date+1). If the patient did not experience any moderate to severe AECOPD events, the event time will be considered as censored at date of EOT or the last contact date within the planned treatment duration. Below is sample SAS code for the Cox regression model:

```
proc phreg data=ttevent;  
class trt01pn eosbgpln cntygr1 nscopd csmoker ppredFev1/ param = glm;  
model aval*cnsr(1) = trt01pn eosbgpln cntygr1 nscopd csmoker ppredFev1;  
estimate "SAR440340 vs Placebo"          trt01pn -1 1 / exp;  
ods output Estimates = Estimates;  
  
run;
```

Similar analysis will be performed for the secondary efficacy population (high EOS group), without the baseline eosinophil strata in the model.

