2.4.4.3.3 Analyses of the other time-to-event endpoints

Time to the expanded AECOPD endpoint and time to first Clinically Important Deterioration (CID) up to week 52 will be analyzed using the same approach as the analysis of the time to first moderate or severe AECOPD. Similar analysis will be performed for the secondary efficacy population (high EOS group), without the baseline eosinophil strata in the model.

2.4.4.3.4 Analyses of actigraphy and home spirometry data (for patients in US and Canada only)

Change from the average of measurements over baseline and the average of measurements over Weeks 10-12 and over Weeks 22-24 in sleep parameters (total sleep time, wake after sleep onset, overnight activity counts) will be summarized (using mean, standard error, min, Q1, median, Q3 and max) in a table.

Similarly, change from the average of measurements over baseline and the average of measurements over Weeks 10-12 and over Weeks 22-24 in activity parameters (daytime activity counts, percent of time spent in sedentary activity, percent of time spent in moderate to vigorous physical activity) will be summarized (using mean, standard error, min, Q1, median, Q3 and max) in a table.

Change from the average of measurements over baseline and the average of measurements over Weeks 10-12 and over Weeks 22-24 in FEV1 (L) measured at home, will be summarized (using mean, standard error, min, Q1, median, Q3 and max) in a table, which will also include the summary of FEV1 (L) values from the in-clinic visits for the same group of patients.

Additional exploratory analyses may be conducted depending on data availability.

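### The Cox code reused for time to first CID names no ties method, so the CID hazard ratio and its interval are pulled slightly toward 1; naming Efron is a free improvement

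*Protocol*

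**What the plan says.** Protocol Section 3, Table 1, lists the endpoint as "Time to first Clinically Important Deterioration (CID) as defined by decrease of >100 mL from baseline in trough FEV1", together with an SGRQ and an exacerbation component. SAP 2.1.3.3 defines CID as a fall of more than 100 mL "in trough pre-BD FEV1 and/or deterioration in SGRQ by 4 units and/or moderate-to-severe AECOPD over the treatment period". SAP 2.4.4.3.3 gives the method: "time to first Clinically Important Deterioration (CID) up to week 52 will be analyzed using the same approach as the analysis" of time to first exacerbation.

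That analysis is in SAP 2.4.4.2.3. A Cox model supplies the hazard ratio and its 95% confidence interval, and a log-rank test stratified by eosinophil stratum and region supplies the p-value. The model statement is "model aval*cnsr(1) = trt01pn eosbgpln cntygr1 nscopd csmoker ppredFev1", with no ties option. Event time is written for exacerbations only, from the "onset date of the first moderate or severe AECOPD-randomization date+1". Neither document says how an FEV1 or SGRQ event is dated, and neither mentions ties or interval censoring.

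On assessment times:

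- **SGRQ** (SAP 2.1.3.3.1): "This questionnaire is assessed at baseline and at weeks 4, 8, 12, 24, 36, 52, 60 and 72".
- **Clinic pre-bronchodilator spirometry** (Protocol 1.3.1): Weeks 2, 4 and 8, then every 4 weeks to Week 52. A footnote adds that "if spirometry is not performed at the scheduled visit it should be performed at the following visit during the treatment period".
- **Visit window** (Protocol 1.3.1): ±3 days during treatment.

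**The concern.** An exacerbation can start on any day, so its onset dates rarely coincide. An FEV1 or SGRQ deterioration can be dated only to a visit, so many patients share an event day. The ties method hardly matters for the first kind of event and does matter for the second.

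When d patients have events on the same day, Breslow uses the full risk-set sum for each of them, so the denominator is [Σ_R exp(βx)]^d. Efron removes the tied cases progressively: Π over l = 0,…,d−1 of [Σ_R exp(βx) − (l/d) Σ_D exp(βx)]. Breslow's larger denominator pulls β toward 0, and the pull grows with d relative to the risk set.

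At stake is the accuracy of the CID hazard ratio and interval, overall and in the high-eosinophil population.

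**Working it through.** **1. The plan's own figures.** The documents give no event count, hazard ratio or power for CID. The nearest figures, in Protocol 9.2 and SAP 1.3, test whether the design inputs are read correctly.

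- *Primary power.* Var(log rate ratio) = 1/I_placebo + 1/I_active, with I = 170 × E[μt/(1 + 1.5μt)] and t taken from the stated accrual and dropout. At a 45% reduction this gives 81.6%, 85.2% and 88.8% for placebo rates 1.0, 1.2 and 1.5, as stated. Mean exposure is 35.5 ± 12.8 weeks, as stated.
- *FEV1 power.* 170 × 0.85 = 144.5 per arm. SE = 0.3 × √(2/144.5) = 0.0353 L. Power = Φ(0.12/0.0353 − 1.96) = 92.5% (92.3% with a t-test; Protocol 92.6%). Least significant difference = 1.96 × 0.0353 = 0.069 L (stated 0.07).

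**2. Where first CIDs come from.** If the Week 24 SD of 0.3 L and difference of 0.12 L held at any one visit, with no mean change on placebo, the chance of crossing the FEV1 limit would be:

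- placebo: Φ(−0.10/0.3) = 37%
- active: Φ(−0.22/0.3) = 23%

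By comparison, the chance of at least one exacerbation by Week 24 at 1.2 per year is 1 − (1 + 1.5 × 1.2 × 24/52)^(−1/1.5) = 33%.

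**3. Simulation inputs.**

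- *From the documents:* 340 patients randomized 1:1, accrual, dropout, exacerbation rate 1.2 per year, dispersion 1.5, FEV1 SD and difference, visit schedules.
- *Assumed:* within-patient correlation 0.6; SGRQ change SD 12, with a 2-unit placebo improvement and a treatment effect of 0-4 units; FEV1 SD 0.2 L as a variant; the spread of visits inside the window.
- *Simplifications:* treatment is the only covariate, and the Week 24 FEV1 SD and effect apply at every visit.

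There were 600-1000 runs per scenario, each dataset fitted by both methods. About 82-86% of first CIDs were visit-detected. The busiest day held about 20 events with evenly spread dates, 51-70 with 50-70% of visits on the target day, and 85-109 with nominal days.

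**4. Breslow against Efron** (FEV1 0.12 L, exacerbations −45%, SGRQ 4 units):

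| Event dates | Breslow HR | Efron HR | HR ratio | Log-scale shift | Shift as share of Efron log HR |
|---|---|---|---|---|---|
| Even over ±3 days | 0.620 | 0.613 | 1.011 | 0.011 | 2.3% |
| 50% on target day | 0.625 | 0.611 | 1.023 | 0.023 | 4.6% |
| 70% on target day | 0.639 | 0.616 | 1.037 | 0.037 | 7.6% |
| All on nominal day | 0.659 | 0.615 | 1.072 | 0.069 | 14.2% |

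The standard error of the log hazard ratio was about 0.12. The shift is therefore about 0.011/0.12 = 0.09 standard errors in the first row and 0.069/0.12 = 0.58 in the last.

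With half-size effects the pairs are 0.800 and 0.795 (even spread) and 0.818 and 0.787 (nominal days). Under an exact proportional-hazards model (placebo CID risk by Week 24 of 50-85%, HR 0.55-0.8) the HR moves by 0.1-0.6% with spread dates and 0.6-3.4% with nominal days.

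**5. With no treatment effect.** Both methods centre on 1. The Breslow Wald test rejected in 1.3-1.8% of runs with nominal days and 4.0% with spread dates, against 4.3-4.8% for Efron. So any distortion lies in the Cox estimate and its Wald interval.

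**The case against.** The strongest objection is that the planned test is untouched. A reader might infer from the Wald results that the CID comparison loses power. The documents do not support that: SAP 2.4.4.2.3 takes the p-value from the stratified log-rank test, which does not depend on the Breslow or Efron choice. A separate simulation (300 runs per setting, unstratified, SGRQ effect 2 units) with all visits on the nominal day gave log-rank power of 95.0%, Efron Wald 94.7% and Breslow Wald 90.3%. This objection stands in full.

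Second, the size depends on dating. The only event-time rule in the SAP uses actual dates, and visits may vary by ±3 days, which favours the low end. This also stands, with one limit. Dosing visits are anchored to a two-week schedule, and SAP 2.5.4 maps spirometry to target days, so neither clustering nor nominal dating is excluded.

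Third, the shift is measured against Efron rather than a known true value, and it is smaller under proportional hazards. The Week 24 FEV1 values may also not hold at early visits. Both points are fair and are reflected in the range given.

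Finally, the code is labelled a sample and was written for exacerbations, and the Breslow default is a property of the software that neither document states. That weakens nothing practical: SAP Section 5 specifies SAS, and no other code or ties method is given for CID.

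**Conclusion.** The point holds as a small, one-directional attenuation of a tertiary hazard ratio and its confidence interval. At the planned effects the shift is about 1% of the hazard ratio with evenly spread actual dates, about 2-4% with half or more of visits on the target day, and about 7% at the extreme of nominal dating. These figures rest on the assumed correlation, SGRQ parameters and date spread, and on using Week 24 FEV1 values throughout.

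A reader might take the nominal-day figure as the expected bias, but nothing in the SAP says CID is dated that way. Nor do the documents show that a Cox model is wrong for CID. The scatter of appointments within the window is not shown to differ between the blinded arms. The primary and key secondary endpoints are unaffected, and SAP 2.4.4.4 makes all p-values nominal. This is a free improvement and does not threaten any main conclusion.

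**What to change.** In SAP 2.4.4.3.3, state that the PHREG model for time to first CID uses TIES=EFRON (or EXACT), including in the high-eosinophil population. State also that an FEV1 or SGRQ event is dated by the actual assessment date, measured from randomization in the same way as exacerbation onset. The cost is one code option and one sentence. No data, design or covariate changes are needed, and the estimate remains a hazard ratio.

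A grouped-time (complementary log-log) or interval-censored model is at most an optional sensitivity analysis. Grouping by visit would coarsen the exacerbation component, which is known to the day, and FEV1 and SGRQ follow different visit schedules.
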